This is a multi-reader methodological study comparing the diagnostic value of 68GaPSMA-HBED-CC PET/CT or 68Ga-PSMAHBED-CC PET/MRI over MRI alone, using histologic confirmation or serial follow-up for up to 3 years as the gold standard for determination of primary prostate cancer or prostatic cancer recurrence/metastasis. Patients at moderate- to high-risk for metastatic disease who are scheduled for (the below outlines the patient cohorts recruited for this study): 1. High risk primary disease with planned surgical extirpation and lymph node dissection (oligometastatic disease) 2. Presumed intermediate or high-risk primary disease with planned targeted prostate biopsy 3. Conventional imaging equivocal or suggestive of metastatic disease, with planned biopsy of presumed metastasis a) PSA less than 0.5 ng/mL b) PSA greater than 0.5 ng/mL 4. Planned focal therapy of intermediate- to high-risk primary lesion. 5. Elevated PSA with no conventional imaging suggestive of metastatic or recurrent disease a) PSA less than 0.5 ng/mL b) PSA greater than 0.5 ng/mL. The purpose of the study is to compare 68Ga-PSMA-HBED-CC PET to conventional MRI. We hypothesize that this will demonstrate the superiority of 68Ga-PSMA-HBED-CC PET to MRI for sensitivity, and the non-inferiority of 68Ga-PSMA-HBED-CC PET to MRI for specificity. This is a paired, case-control design that is appropriate to statistically evaluate the difference in sensitivity and specificity between the two imaging modalities. Therefore, the estimation of Therefore, the estimation of population prevalence is not a study objective, and estimation of clinical utility through calculation of positive and negative predictive

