The primary endpoint is to assess the sensitivity and specificity on per-subject basis between the diagnosis from MRI and 68Ga-PSMA-HBED-CC. Based on the previous literature, we anticipate a 0.58 sensitivity and a 0.82 specificity that are consistent across all seven scenarios based on MRI. Here, we first assume that an increase in sensitivity of 30%, i.e. 0.75 under 68Ga-PSMA-HBED-CC will provide little benefit over existing MRI approach. Therefore, our statistical test for 68Ga-PSMA-HBED-CC sensitivity will be based on the null hypothesis of a value as 0.58 with the alternative hypothesis of at least 0.75. The sample size calculation is based on a Wald-test statistic under an arcsine transformation of proportion and an effective size 0.36. As a result, a sample of 34 true positive patients will give us 80% power to reject the null hypothesis at a onesided 0.1 significance level. In terms of specificity, we will expect a non-inferior performance from 68Ga-PSMA-HBED-CC compared with MRI. By assuming delta to be the estimated difference in the specificity between MRI and 68Ga-PSMA-HBED-CC, the statistical test for this metric will be constructed under the null hypothesis that the actual difference is larger than delta and the alternative hypothesis of that is smaller or equal to delta. The test statistic will asymptotically follow a normal distribution based on based on a restricted maximum likelihood estimation approach with the sample size obtained by a Wald-test statistic. Assuming delta=0.15, a sample of 12 true negative (TN) patients will allow us 80% power for this a one-sided 0.1 significance level test. In summary, we need a total of 46 patients (34 TP, 12 TN) for each scenario, leading to a total of 322 patients. Since we expect a 20% drop-off rate, we therefore intend to recruit 402 subjects. The sensitivity and specificity for the diagnosis under 68Ga-PSMA-HBED-CC and MRI on a per patient basis will be summarized as descriptive statistics and the two-sided 90% confidence intervals (CIs) will be constructed using the Wilson score method. The superior of 68Ga-PSMA-HBED-CC MRI for detection of metastatic prostate cancer will be determined if two of the three readers show statistically significantly better performance on sensitivity based on the McNemar test of discordant pairs for subjects and a non-inferiority specificity performance based on overlapped confidence intervals. The lesion-level data will be analyzed by McNemar's test adjusted for clustered data (each subject will contribute at least one lesion result, and possibly many lesion results). Published methods will be used for the lesion-level analyses (Durkalski et al, Statist. Med. 2003; 22:2417-2428 "Analysis of clustered matched-pair data"; Statist. Med. 2003; 22:279-290 "Analysis of clustered matchedpair data for a non-inferiority study design"). Reader-specific sensitivities and specificities will be calculated primarily for patient-based results for lymph nodes of any size. Sensitivity and specificity calculations will be performed for each imaging modality with the CIs calculated based on Wilson score method. In addition, we will assess 68Ga-PSMA-HBED-CC PET and MRI image data for cancer staging and compare their performance based on a Wilcoxon signed-rank test. And finally, safety of the 68Ga-PSMA-HBED-CC test will be assessed by tabulation of any procedure-related adverse effects.

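### Non-inferiority of specificity is sized as a test against a 0.15 margin but decided by overlapping confidence intervals, a rule with no margin that at 12 true negatives passes a PET at the margin about 95% of the time or more; the assumptions behind the 12 are also not stated

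*Combined protocol and SAP*

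**What the plan says.** Everything except the design statement is in the unnumbered statistical and sample-size paragraph that closes the combined protocol and SAP.

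- Design (Study Design section): "This is a paired, case-control design that is appropriate to statistically evaluate the difference in sensitivity and specificity between the two imaging modalities".
- MRI inputs: "we anticipate a 0.58 sensitivity and a 0.82 specificity that are consistent across all seven scenarios based on MRI".
- Specificity hypotheses: "the null hypothesis that the actual difference is larger than delta and the alternative hypothesis of that is smaller or equal to delta".
- Test and sizing method: "restricted maximum likelihood estimation approach with the sample size obtained by a Wald-test statistic".
- Sample size: "Assuming delta=0.15, a sample of 12 true negative (TN) patients will allow us 80% power for this a one-sided 0.1 significance level test". With 34 true positives this makes 46 per scenario, 322 over seven scenarios and 402 to be recruited.
- Intervals: "the two-sided 90% confidence intervals (CIs) will be constructed using the Wilson score method".
- Success: superiority "will be determined if two of the three readers show statistically significantly better performance on sensitivity", by McNemar's test, together with "a non-inferiority specificity performance based on overlapped confidence intervals".

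No number is given for PET specificity or for the proportion of true negatives on which PET and MRI disagree. The plan does not say whether the success rule applies within each scenario or to the pooled patients.

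**The concern.** Non-inferior specificity is one of two conditions for the claim the study wants to make. The plan sets up a test of it against 0.15 and then leaves that test out of the decision. Overlap of two intervals shows only that no large difference was detected. It gets easier as the sample shrinks, so it rewards imprecision, whereas a non-inferiority test penalises it. A PET that misses the plan's own margin could be declared non-inferior almost by default.

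A second, lesser matter is the 12 itself. In a paired design the sample size depends on both specificities and on the discordance, and only MRI specificity is stated. The 12 feeds the 46, 322 and 402, so the specificity part of those totals has no stated justification.

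**Working it through.** **Inputs from the plan.** MRI specificity 0.82; delta 0.15, read as the margin; one-sided 0.1; power 80%; 12 true negatives per scenario; seven scenarios, so 7 × 12 = 84 if pooled; 90% Wilson intervals. **Assumed, because not stated:** PET specificity and discordance, shown over a range. All rates below are for one reader and for specificity only.

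**1. Can the 12 be reproduced?** (z0.90 + z0.80)² = (1.2816 + 0.8416)² = 4.508.

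- MRI fixed, PET also 0.82: 4.508 × 0.82 × 0.18 / 0.15² = 29.6, so 30.
- Independent reads, PET also 0.82: 4.508 × 2 × 0.82 × 0.18 / 0.15² = 59.1, so 60.
- Paired Wald: n = 4.508 × (pd − d²) / (0.15 + d)², where pd is discordance and d is PET minus MRI specificity. With d = 0 and pd = 0.06: 4.508 × 0.06 / 0.0225 = 12.0.
- MRI fixed, PET 0.874: 4.508 × 0.874 × 0.126 / 0.204² = 11.9, so 12.

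So 12 is reachable, but only with an added assumption that the plan does not state. By contrast, the sensitivity figure does follow from its stated inputs: the arcsine effect size for 0.58 against 0.75 is 0.363, and 4.508 / 0.363² = 34.2, against the plan's 34.

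**2. How does the overlap rule behave?** PET passes if its upper 90% Wilson limit is at or above MRI's lower limit. Enumerating every paired 2 × 2 table at n = 12 with MRI 0.82 gives:

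| True PET specificity | Discordance | Passes |
|---|---|---|
| 0.67 (at the margin) | 0.391 (independent) | 94.5% |
| 0.67 | 0.25 | 97.7% |
| 0.67 | 0.20 | 98.5% |
| 0.67 | 0.15 | 99.2% |
| 0.52 (twice the margin) | 0.487 (independent) | 79% |
| 0.52 | 0.30 | 86% |

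Independence at PET 0.67 means 0.82 × 0.33 + 0.67 × 0.18 = 0.391. A valid test would pass PET at the margin about 10% of the time.

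A single result shows the same thing. MRI correct in 10/12 has lower limit 0.601, and PET correct in 5/12 has upper limit 0.644. The intervals overlap, so PET counts as non-inferior although the observed difference is 5/12 = 0.42. PET first fails at 4/12 (upper limit 0.569).

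With 84 pooled true negatives, PET at 0.67 passes 53% (independent reads) to 57% (discordance 0.15). PET at 0.52 passes 3% or less.

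**3. What would the plan's own test do at n = 12?** The cut-off is 1.2816. With no discordant pairs the restricted variance is 0.15 × 0.85 = 0.1275, so z = 0.15 × √12 / √0.1275 = 1.455, a pass. One discordant pair against PET gives z = 0.65, a fail.

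- Size at the margin: at discordance 0.15 every discordant pair is against PET, so the test passes only with none: 0.85¹² = 0.142. At discordance 0.20 and 0.30 the size is 0.110 and 0.097.
- Power at equal specificity (0.82): 0.71, 0.58, 0.42 and 0.35 at discordance 0.06, 0.10, 0.20 and 0.295 (independence).
- Power with PET better: 0.85 (PET 0.85, discordance 0.06), 0.70 (0.85, 0.10), 0.91 (0.90, 0.10) and 0.67 (0.90, 0.20).

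**The case against.** **Scope.** The 12 is set per scenario, but the success sentence makes a single claim, so the sponsor may intend one pooled analysis. The rates near 95% and the result at twice the margin would not then apply. That stands, and both must be read as per-scenario figures. Pooling does not rescue the rule, since a 53% to 57% pass rate at the margin is still far from 10%.

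**The 12.** A reader might infer that 12 is an arithmetic error or that 80% power is refuted. The documents do not support that. The plan sizes sensitivity against a fixed MRI value, and the same convention gives 12 for specificity at PET about 0.874. The named test also exceeds 80% power at some plausible points, such as 0.85 at PET 0.85 with discordance 0.06. The 80% is unsupported rather than disproved, and this part is a documentation gap.

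**Overall error.** A reader might also infer that the study would wrongly declare success about 95% of the time. It would not: success also requires McNemar's test on sensitivity, and two of three readers. The rates here describe one reader and one condition.

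**Exact tests.** The plan names an asymptotic test. Using it in place of overlap brings the pass rate at the margin from about 0.95 or more down to at most 0.142 at n = 12, which already repairs the main defect. An exact version is an option, not a requirement.

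**Conclusion.** The main point holds: the test that is sized and the rule that decides are different, and the deciding rule cannot support a claim of non-inferiority at 0.15. This does not depend on which assumptions produced the 12. The size of the problem depends on scope: a 94.5% to 99.2% pass rate at the margin per scenario with independent or positively correlated reads, or about 53% to 57% pooled, against a nominal 10%. These figures assume MRI specificity 0.82 as the plan states.

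The secondary point holds as a reporting gap only. The 12 does not follow from the stated inputs, and the unqualified 80% is true under some unstated assumptions and well short under others.

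**What to change.** 1. In the success rule, replace overlap of the intervals with the paired restricted-likelihood non-inferiority test against 0.15 at one-sided 0.1 that the same section already describes, applied per reader. Keep the Wilson intervals as description.
2. Say whether the rule applies within each scenario or to pooled patients.
3. If the test is applied at n = 12, state that its actual size reaches 0.142 (at discordance 0.15) or, optionally, use an exact version.
4. State the PET specificity, the discordance and the formula or software behind the 12. Replace the unqualified 80% with the named test's single-reader power at n = 12 over a range, for example 0.71, 0.58, 0.42 and 0.35 at equal specificity with discordance 0.06, 0.10, 0.20 and 0.295, and 0.85 at PET 0.85 with discordance 0.06.

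Cost: the correction adds no patients. It is nevertheless a change to the primary success criterion: specificity becomes harder to pass and the stated power less favourable. Whether to enlarge the true-negative group in response is a separate decision for the sponsor.

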3. Pathologic confirmation of adenocarcinoma of the prostate gland or high clinical suspicion (PSA > 4 ng/mL, or PSA density > 0.15 ng/mL2, or PSA doubling time < 2 years).
4. Meet one of the following 5 Criteria:
 - a. Planned for surgical extirpation, which may or may not include lymph node dissection (high risk primary disease)
 - b. Planned for targeted biopsy of primary lesion
 - c. Conventional imaging equivocal or suggestive of prostate cancer metastasis/es
 - d. Planned focal therapy (with or without radiation therapy) with serial follow-up
 - e. Elevated PSA with no conventional imaging suggestive of metastatic or recurrent disease

5. a. If part of PET/MRI cohort, subject will undergo clinically indicated MRI imaging prior to treatment.
Or b. If part of PET/CT cohort, subject will have had clinically indicated MRI within 3 months prior to treatment.

6. Participants must agree to use an acceptable form of birth control throughout the study period. Participants must use condoms for a period of seven days after each injection, if engaged in sexual activity."

EXCLUSION CRITERIA

1. Clinical and/or technical factors that would compromise statistical analysis of the PET and/or MRI.
2. If part of PET/MRI cohort and patient cohort 3 or 5, subject does not plan to have a prescribed abdomen2/ MRI
3. If part of PET/MRI cohort and patient cohort 1, 2 or 4, subject does not plan to have a prescribed pelvis MRI
4. If part of PET/CT cohort and patient cohort 3 or 5, subject does not have previous MR imaging of abdomen and pelvis
5. If part of PET/CT cohort and patient cohort 1, 2 or 4, subject does not have previous MR imaging of pelvis
6. If part of PET/CT cohort, investigator review determines that previous MR images do not meet institutional quality standards
7. If part of PET/MRI cohort, contraindications to MRI
8. Contraindications to PSMA IV administration
9. Other unspecified reasons that, in the opinion of investigators, make the subject unsuitable for enrollment

DATA AND SAFETY MONITORING PLAN

Data is recorded both electronically and in paper format Data will be kept in the PIs locked office Data will be kept on a password-protected computer Data will be saved on a secure server.

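### 80% power is claimed in each of seven scenarios on a 34:12 split of reference-positive to reference-negative patients, but the plan gives no prevalence, no mechanism to reach the split and no target condition per cohort

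*Combined protocol and SAP*

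**What the plan says.** The unnumbered statistical section sizes each scenario in two parts: 34 patients for sensitivity (0.58 under the null, 0.75 under the alternative) and 12 for specificity (margin 0.15), each at 80% power and one-sided 0.1. It adds and multiplies them: "In summary, we need a total of 46 patients (34 TP, 12 TN) for each scenario, leading to a total of 322 patients". TP and TN here can only mean reference-positive and reference-negative. A 20% drop-off allowance takes the total to 402. The seven scenarios match cohorts 1, 2, 3a, 3b, 4, 5a and 5b of the Study Design section.

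On how patients are sampled, Study Design says: "This is a paired, case-control design that is appropriate to statistically evaluate the difference in sensitivity and specificity between the two imaging modalities". It adds that "the estimation of population prevalence is not a study objective".

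On entry, Study Design and the inclusion criteria select by clinical situation. Cohort 4, for example, is "Planned focal therapy of intermediate- to high-risk primary lesion". Inclusion criterion 3 asks for "Pathologic confirmation of adenocarcinoma of the prostate gland or high clinical suspicion".

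On the target condition, Study Design sets the gold standard, histology or serial follow-up for up to three years, for "determination of primary prostate cancer or prostatic cancer recurrence/metastasis". The statistical section words its success rule for metastatic disease only, and says the reader-specific estimates are primarily patient-level nodal results.

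**The concern.** Power for sensitivity depends on how many reference-positive patients a scenario yields, and power for specificity on how many reference-negative ones. With 46 evaluable patients, both 80% figures hold together only near a 34:12 split. The plan names that split as a need but does not say why any cohort should produce it, let alone all seven. Reference status is generally settled after the scan, so it cannot readily be used to select patients.

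Because the target condition is not assigned by cohort, positive and negative are not defined by cohort either. At stake is whether each scenario can support the sensitivity and specificity conclusions that the plan says it is powered for.

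**Working it through.** **1. Reproduce the plan's figures.** Inputs from the statistical section: 0.58, 0.75, one-sided 0.1, 80% power, arcsine scale.

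- Effect size h = 2(asin √0.75 − asin √0.58) = 0.363; the plan states 0.36.
- n = ((1.2816 + 0.8416)/0.363)² = 34.2. Power at n = 34 is Φ(0.3629 × √34 − 1.2816) = 79.8%. The stated 34 and 80% reproduce.
- 34 + 12 = 46; 46 × 7 = 322; 322/0.8 = 402.5, against 402 stated.
- The 12 for specificity is taken as given; how it was derived is not examined here.

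**2. Implied prevalence.** 34/46 = 73.9% in every scenario.

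**3. Effect of other prevalences.** The documents give none, so p is an assumption, shown from 30% to 95%. With 46 evaluable patients, the number of positives X is Binomial(46, p). Average sensitivity power is the mean of Φ(0.3629√X − 1.2816) over X. Expected negatives are 46(1 − p).

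| Assumed prevalence | Expected positives | Average sensitivity power | Expected negatives |
|---|---|---|---|
| 30% | 13.8 | 52% | 32.2 |
| 50% | 23.0 | 67% | 23.0 |
| 60% | 27.6 | 73% | 18.4 |
| 70% | 32.2 | 78% | 13.8 |
| 73.9% | 34.0 | 80% | 12.0 |
| 80% | 36.8 | 82% | 9.2 |
| 90% | 41.4 | 85% | 4.6 |
| 95% | 43.7 | 87% | 2.3 |

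The drop-off allowance does not change this. With 57 enrolled per scenario (402/7 = 57.4) and 20% lost, X is Binomial(57, 0.8p), and power is 79% at 73.9%, 78% at 70%, 73% at 60%, 67% at 50% and 52% at 30%.

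**4. Precision of specificity.** At an observed specificity of 0.82, the plan's Wilson 90% interval is 0.59–0.94 with 12 negatives, 0.55–0.95 with 9 and 0.45–0.96 with 5.

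**5. Target condition: three readings set against the cohorts.**

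- Prostate cancer. The extirpation and focal-therapy cohorts would probably supply few or no negatives. Criterion 3 admits some patients on suspicion alone, so the number need not be zero.
- Metastasis. About 74% of every cohort, including patients planned for focal therapy, would have to be metastatic.
- A target that varies by cohort, which the gold-standard sentence in Study Design allows. The success rule, worded for metastatic disease only, then contradicts it.

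None of the three makes 34:12 a natural expectation in all seven cohorts.

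**The case against.** The best defence is the case-control label: sampling on disease status fixes the split by design, and prevalence then does not matter. That would be right if such sampling were described. It is not. Not having prevalence as an objective also does not remove the need for a planning value, because prevalence decides how many positives and negatives a cohort yields.

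Several limits do stand.

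- The 34 and 12 can be read as a target by status. What is missing is a means of reaching it.
- Study Design restricts entry to patients at moderate to high risk of metastasis and describes cohort 1 as "High risk primary disease with planned surgical extirpation and lymph node dissection (oligometastatic disease", so a metastasis target is less implausible there than in focal therapy.
- Focal-therapy patients may have an optional post-treatment PET/MRI, which could yield negative scans. The plan does not say that these enter the primary analysis.
- Nothing in the documents shows that any cohort lies at 50% prevalence or below, where sensitivity power falls furthest.

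A reader might infer that specificity cannot be assessed once prevalence exceeds 74%. The figures do not support that: at 80% about 9 negatives are expected and the interval is only slightly wider than planned. A reader might also infer that a shortage of negatives is what makes the overlapping-interval criterion for non-inferiority lenient. That criterion is already lenient at the planned 12: MRI 10/12 (0.60–0.94) and PET 5/12 (0.22–0.64) overlap despite a 42-point drop. It is a separate defect, and securing the split would not cure it.

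**Conclusion.** The concern holds in this form: the plan states 80% power per scenario for sensitivity and for specificity, but secures neither the split on which those figures rest nor a consistent definition of positive and negative. The omission is clear from the text. Its size is conditional on prevalence, which is assumed throughout.

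At 70% prevalence the sensitivity loss is about two points. It becomes material further away: 67% power at 50%, 52% at 30%. On the other side, specificity becomes inestimable only where negatives are nearly absent.

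The power figures use the plan's one-sample arcsine formula. Power under the actual success rule, McNemar's test in two of three readers, is not computed, and specificity power is not recalculated. The documents do not support the stronger conclusion that the trial, or any named scenario, is underpowered; they support only that the claimed power cannot be relied on as stated.

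**What to change.** - State the target condition and reference standard for each cohort, and make the success rule in the statistical section match.
- Replace the unconditional 80% per scenario with power for sensitivity and for specificity at the expected positive and negative counts, over a stated prevalence range for each scenario.
- Report scenarios not expected to reach the counts descriptively, with confidence intervals. Make no per-subject specificity claim in a cohort that cannot supply reference-negatives.
- If cohorts are pooled, pool only those that share a target condition.
- Reconcile the case-control label with how patients are actually enrolled.

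The cost is protocol and SAP wording and a restated power calculation, with no extra patients. The downside is losing the per-scenario power claim, and the specificity claim in cohorts without negatives.

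The sponsor could instead keep the split by enrolling until both counts are met. The mean number of evaluable patients needed per scenario, summing over n the probability that either count is still unmet, is about 52 at 74% prevalence, 57 at 60%, 68 at 50% and 120 at 90%, against 46 planned. Enrolment would also have to wait on reference status that may take up to three years to settle.

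### The success rule judges specificity by overlapping confidence intervals instead of the 0.15 margin test: at 12 true negatives, PET exactly 0.15 worse passes about 95–98% of the time per reader, against an intended 10%

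*Combined protocol and SAP*

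**What the plan says.** All of this is in the statistical paragraph on the primary endpoint, which closes the combined protocol and SAP.

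- **Hypothesis.** For specificity, "the statistical test for this metric will be constructed under the null hypothesis that the actual difference is larger than delta".
- **Statistic and sizing.** The test is asymptotically normal and rests on "a restricted maximum likelihood estimation approach with the sample size obtained by a Wald-test statistic".
- **Sample size.** "Assuming delta=0.15, a sample of 12 true negative (TN) patients will allow us 80% power for this a one-sided 0.1 significance level test". Then "we need a total of 46 patients (34 TP, 12 TN) for each scenario, leading to a total of 322 patients".
- **Anticipated value.** MRI is expected to have "0.82 specificity that are consistent across all seven scenarios based on MRI". No such consistency is stated for PET.
- **Intervals.** For each modality, "the two-sided 90% confidence intervals (CIs) will be constructed using the Wilson score method".
- **Success.** Superiority "will be determined if two of the three readers show statistically significantly better performance on sensitivity" by McNemar's test, together with "a non-inferiority specificity performance based on overlapped confidence intervals".

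The opening background text names non-inferior specificity as one of the two claims to be demonstrated. The Study Design section calls the design paired.

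**The concern.** The paragraph holds two specificity criteria and does not reconcile them. The first has a margin, an error rate and a sample size. The second, in the only sentence that defines success, has none of these.

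Overlap of two separate intervals shows only that the data failed to pull them apart. It sets no limit on how much worse PET may be. It takes no account of both modalities being read in the same patients. Fewer patients give wider intervals and so an easier pass, which is the reverse of what a non-inferiority criterion should do. If the success sentence is followed, success can be declared without any comparison with 0.15.

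The text also leaves open whether the rule applies within each scenario, and whether the same two of three readers must meet both the sensitivity and the specificity parts. A smaller point is that delta is introduced as an estimated difference and then fixed at 0.15.

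**Working it through.** **Inputs from the plan.** MRI specificity 0.82; margin 0.15, so PET at the margin is 0.82 − 0.15 = 0.67; 12 TN; one-sided 0.10; 80% power; two-sided 90% Wilson intervals (z = 1.645).

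**Assumed.** The within-patient PET–MRI correlation ρ among TN patients is not given. I use 0, 0.3 and 0.5 and also show the feasible range, which at 0.82 and 0.67 is −0.33 to 0.67.

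**The plan's own figure.** A paired Wald formula gives n = ψ(1.2816 + 0.8416)²/0.15² = 200.35ψ, where ψ is the proportion of discordant patients. With ψ = 0.06, n = 12.02. With independent readings ψ = 2 × 0.82 × 0.18 = 0.295 and n = 59.1. The plan states no ψ, so 12 can be neither confirmed nor called wrong.

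**The overlap rule at 12 TN.** The Wilson interval for x/12 with p = x/12 is [p + 2.706/24 ± 1.645√(p(1−p)/12 + 2.706/576)]/(1 + 2.706/12). Specificity passes when the PET upper limit is at or above the MRI lower limit:

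| MRI correct | MRI lower limit | Fewest PET correct that still passes |
|---|---|---|
| 12/12 | 0.816 | 8/12 |
| 11/12 | 0.699 | 6/12 |
| 10/12 | 0.601 | 5/12 |
| 9/12 | 0.513 | 4/12 |

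For example, 11/12 gives 0.699–0.981 and 6/12 gives 0.286–0.714, so PET counts as non-inferior. The paired upper one-sided 90% score limit for that drop is 0.598 (discordant pairs 5 and 0) or 0.624 (6 and 1), against a margin of 0.15.

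**Pass rate when PET is exactly 0.15 worse.** The probability that both modalities are correct is 0.82 × 0.67 + ρ√(0.82 × 0.18 × 0.67 × 0.33) = 0.5494 + 0.1807ρ. The other three cells follow by subtraction. Summing the multinomial probabilities exactly over all passing outcomes, for one reader:

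| TN | ρ = 0 | ρ = 0.3 | ρ = 0.5 |
|---|---|---|---|
| 6 | 0.970 | 0.985 | 0.992 |
| 12 | 0.945 | 0.970 | 0.984 |
| 48 | 0.741 | 0.780 | 0.819 |
| 84 | 0.531 | 0.538 | 0.548 |

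At 12 TN the range over all feasible ρ is 0.919 to 0.992. The row of 84 (7 × 12) is a sensitivity case only, as the plan describes no pooled test; at the maximum ρ it is 0.566.

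**Readers.** If all three readers share these specificities, the chance that at least two pass specificity is at least 1 − 1.5(1 − p), whatever the dependence between readers. With p = 0.945 this is 0.918; with p = 0.919 it is 0.878.

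**Joint with sensitivity.** True-positive and TN patients are different people, so one reader's joint rate is a product. If sensitivity passed 80% of the time (an assumption; the plan's 80% belongs to a test against a fixed 0.58, not to McNemar), it would be 0.80 × 0.945 to 0.80 × 0.984, or 0.76 to 0.79. A true 10% test would give 0.80 × 0.10 = 0.08.

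**The margin test at 12 TN, for comparison.** Let b be the patients whom only MRI reads correctly and c those whom only PET reads correctly. The paired score statistic is (12 × 0.15 − (b − c))/√(12(2q + 0.15 − 0.15²)), where q is the restricted maximum likelihood estimate of the probability behind c. It passes at 1.2816 or more.

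- Error at the margin: 0.096, 0.098 and 0.107 at ρ = 0, 0.3 and 0.5. It reaches 0.142 at maximum concordance, where passing requires no PET-only error: 0.85¹² = 0.142.
- Power with both specificities 0.82: 0.353, 0.412, 0.482, 0.709 and 0.803 at ρ = 0, 0.3, 0.5, 0.8 and 0.875. The corresponding ψ is 0.295(1 − ρ): 0.295, 0.207, 0.148, 0.059 and 0.037.

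**The case against.** The strongest reply is that the margin test is itself written as a planned analysis, with a statistic, a margin and a level, so the overlap phrase may be loose shorthand for it, or an extra screen inside the superiority declaration. That is possible, and the pass rates above apply only if the success sentence is followed as written. But no section says so, and the readings differ between roughly 10% and 95%, so the governing one must be named before analysis.

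The success sentence also speaks of detecting metastatic disease, while some cohorts concern primary lesions. It may therefore not apply in every scenario, and 12 TN is then an assumption for it. This stands as a limit on the headline figure, which is the per-scenario case. It does not rescue the rule: even 84 pooled TN pass 0.53 to 0.57 of the time for ρ from 0 to its maximum.

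McNemar's test on sensitivity must also succeed, so these are not trial-level false-success rates. That is right, but sensitivity is measured in other patients and gives no protection against poor specificity.

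Finally, the plan does not say that its restricted-likelihood test is paired. Putting it in paired form is a choice, which the stated paired design supports.

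**Conclusion.** The concern holds and must be fixed before analysis. As worded, the success sentence replaces a 0.15 margin test with a criterion that screens out almost nothing at 12 TN: a PET exactly at the margin passes 0.945 to 0.984 of the time per reader, against an intended 0.10. This rests on the plan's 0.82 for MRI, on reading overlap as overlap of the two 90% Wilson intervals, on 12 TN per scenario, and on an assumed correlation of 0 to 0.5. No feasible correlation brings the rate below 0.919. The figure covers the specificity component alone.

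**What to change.** In the success sentence, replace overlap with the plan's own margin test in paired form: specificity is non-inferior if the upper one-sided 90% restricted-likelihood (score) limit for MRI minus PET specificity is below a fixed 0.15. Describe delta as a fixed margin. Keep the Wilson intervals as descriptive. State whether the rule applies per scenario, and whether the same two of three readers must meet both parts. State the assumed discordance and restate the power at 12 TN.

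The rule is a text change, but non-inferiority becomes harder to claim. At 12 TN, equal observed specificities with one discordant patient each way already fail (upper limit 0.179), and 80% power needs a correlation of about 0.875 or more, that is, discordance of about 4% or less. For 80% power with the score test, TN per scenario would be about 62, 44, 34 or 21 at ρ = 0, 0.3, 0.5 or 0.8.

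Either acknowledge that the asymptotic test's error at 12 TN can reach about 14% at high concordance, or use an exact test and justify the TN number for it. An exact 10% test cannot pass at 12 TN even when the two modalities agree in every patient, because 0.85¹² = 0.142. It needs at least 15 TN for that (0.85¹⁵ = 0.087). Pooling scenarios to gain TN patients would need its own justification, since consistent specificity is assumed only for MRI.
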